If patients are not able to use the app for any reason, a text message and/or email will be sent to the patient each evening via the REDCap™ (Research Electronic Database) website that will ask questions about the frequency and severity of epistaxis and energy level that replicates the Cure HHT app. The REDCap™

survey will assess for compliance by asking if the research subject has used the assigned treatment that day. Once each week, the survey will ask the subject if he or she received a blood transfusion that week. REDCap™ is a password-protected site that will keep the information confidential.

Methods

Demographic information, including age, gender, and race, will be collected from each enrolled patient. Data will be collected regarding the duration of each patient's epistaxis history, previous treatments, and estimation of the average number of nosebleeds per day; HHT treatment history; co-morbid conditions, such as hypertension, inhalant allergies, and other blood dyscrasias; risk factors, such as cigarette smoking, use of CPAP, and use of supplemental oxygen; and medications associated with increased bleeding.

At the initial visit, research subjects will complete the informed consent process, *SF-36*, *ESS*, baseline electrocardiogram (ECG), CYP2D6 enzyme allele, blood pressure (BP), and heart rate (HR). ECGs are to be read by [name]. Subjects will undergo a directed otolaryngology physical exam by [name] that will include nasal endoscopy to describe nasal mucosa telangiectasias. [name] will rate the nasal mucosa telangiectasias using the *HES*. Patients will be scheduled for phlebotomy to obtain a blood specimen to measure hemoglobin levels prior to beginning therapy. Baseline daily iron supplementation will also be recorded and it will be recommended to the patient not to alter their daily supplementation of iron or other treatments, unless indicated by a change in epistaxis frequency.

Upon demonstration that patient does not have the CYP2D6 allele associated with a low or intermediate metabolizer of timolol and successful completion of questionnaires, physical examination, and laboratory tests, subjects will be randomized to receive either timolol gel or placebo.

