Pharmaceutical Preparation. The intervention will be prepared and dispensed by Advanced Rx Pharmacy, Plymouth Meeting, Pennsylvania. Timolol nasal gel 0.1% will be prepared with a poloxamer gel (combination of poloxamer 188 and 407; pH adjusted to 4.5-6.5) and 0.5 ml applied to each nostril twice daily. The total daily dose would amount to 2 mg. Placebo gel is prepared with poloxamers and no active ingredients. Timolol is odorless so the research subjects should not be able to identify the placebo gel from the active gel.

Subjects will be instructed to apply 0.5 ml to the nasal mucosa of each nostril twice daily via 20 mL syringes. The gel will be dispensed in an amber vial with an adapter to which the syringe can attach in order to draw out the medication for each dose. Patients will be supplied with one syringe per day for a total of 56 syringes. They will be given alcohol wipes to clean the syringe between the morning and evening gel application. When the syringes are distributed, the research assistants will make sure that the patient understands how to apply correctly the medication to the nasal cavity.

BP and HR measurements will be obtained by the subject weekly at home with the use of the blood pressure monitor given to them at the beginning of the study and blood pressures will be reported via the use of REDCap™. Subjects will also be instructed to report any local or systemic side effects throughout the duration of the study. Telephone calls with the study team at the end of Week 1 and again at Week 4 will be arranged.

After 8 weeks of intervention, subjects will be asked to return to clinic and the physician will perform nasal endoscopy and complete the *HES* scale. Subjects will have blood pressure and heart rate measurements. Subjects will complete the *SF-36*, *ESS*, *CGI*, *EQQoL*, and the *TSQMII* questionnaires. To assess the quality of the blind, subjects will be asked which arm of the study they thought they were randomized. Subjects

will also be asked whether they would recommend the treatment to a friend or family member if they suffered with HHT-associated epistaxis. A follow-up blood draw to measure hemoglobin and hematocrit will be completed.

It will be emphasized to the patient not to change their current nasal hygiene regimen (e.g., nasal saline spray) or other chronic treatments (e.g., tranexamic acid).

[figure not shown]
Primary Outcome:

- 1) Mean change in Epistaxis Severity Score (ESS) between baseline and follow-up.

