Secondary Outcomes:

- 1) Clinical Global Impression – Improvement (CGI-I) Score
- 2) Mean change in hemoglobin
- 3) Change in intensity of telangiectasias in the nasal mucosa as determined by the HHT endoscopic scale (HES)

Summary of Project Design

VIII. SAMPLE SIZE AND PLANNED STATISTICAL ANALYSIS

Sample Size

Sample size estimate for the proposed study were derived from the single study(Ichimura et al. 2016) of within subject change in severity of epistaxis associated with timolol ophthalmic solution (0.5%) as a nasal drop. In that study, 9 of the 11 subjects (82%) experienced a reduction in the severity of bleeds as measured on a 5-point Likert scale. We hypothesize a similar response (82%) in our proposed study among subjects randomized to receive timolol gel and a 20% response rate among subjects randomized to placebo gel, corresponding to a difference of 62%.

A power analysis was performed using Fisher’s exact test in G-Power 3.1.2. We estimate that a total sample size of 24 patients (ie., 12 in each arm) is needed to allow us to detect with 80% power at the 2-sided alpha level of 0.05 a difference of 62% or more in the percent of subjects who experience reduction of severity of

bleeds between treatment groups. Considering a 20% drop out rate, we plan to enroll 30 subjects in the study.

Statistical Analysis

Standard descriptive statistics will be used to describe distribution of baseline characteristics in each of the study groups. The effect of the intervention will be measured as the difference in the within-subject change (baseline – 8-week follow-up) in *ESS* scores between the two treatment groups calculated as shown below.

1) Within subject difference with each treatment group

$$\begin{aligned}\Delta ESS_{\text{Timolol}} &= (ESS_{\text{Timolol_base}} - ESS_{\text{Timolol_8-Week}}) \\ \Delta ESS_{\text{Control}} &= (ESS_{\text{Timolol_base}} - ESS_{\text{Timolol_8-Week}})\end{aligned}$$

2) Between treatment difference

$$\Delta ESS_{\text{Timolol}} - \Delta ESS_{\text{Control}}$$

The 95%CI around this effect size will be determined to assess the precision of the observed effect and whether a clinically meaningful difference is plausible given the observed results.

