An independent sample t-test will be used to compare the change in scores between the two study groups. If potential confounding factors are identified, a mixed model analysis will be employed to compare the change in the scores between the two study groups after controlling for potential confounding factors.

Appropriate analyses will be performed for the secondary outcome measures.

IX. EXEMPTION FROM IND REQUIREMENTS

The use of timolol in topical nasal gel is a change in the approved route of administration. An exemption from IND requirements will be requested as the proposed use of timolol in this study fulfills all of the criteria for exemption.

- 1) Timolol is lawfully marketed in the United States.
- 2) This study is not intended to be reported to the FDA in support of a new indication or significant change in labeling.
- 3) This study is not intended to support a significant change in the advertising for the drug.
- 4) The study does not involve a route of administration, dose, patient population, or other factor that significantly increases the risk (or decreases the acceptability of the risk) associated with the use of timolol.
- 5) The study will be conducted in compliance with the requirements for review by an IRB (21 CFR part 56) and with the requirements for informed consent (21 CFR part 50).
- 6) The study is not intended to promote or commercialize timolol.

X. ASSESSMENT OF TREATMENT SAFETY

Treatment Safety

Treatment safety information comes from three different sources. First, a study was conducted to assess the properties of 1% (10 mg) topical intranasal timolol gel and to optimize controlled release *in situ* nasal

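### A prespecified ANCOVA on baseline ESS would be a cheap improvement, of small and uncertain size, on the change-score t-test with its conditional mixed model

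*Combined protocol and SAP*

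**What the plan says.** Section VIII, Statistical Analysis, defines the effect from each subject's change: "The effect of the intervention will be measured as the difference in the within-subject change", taken as baseline minus 8-week ESS. The test follows: "An independent sample t-test will be used to compare the change in scores between the two study groups". The next sentence begins "If potential confounding factors are identified, a mixed model analysis will be employed" and describes a comparison of the same change scores controlling for those factors. It does not name the factors, say how or when they are identified, or state which result leads if the two disagree. The 95% CI is to show "whether a clinically meaningful difference is plausible given the observed results".

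Section VII, Methods, has the ESS completed at the initial visit and again after 8 weeks ("Subjects will complete the *SF-36*, *ESS*, *CGI*, *EQQoL*, and the *TSQMII* questionnaires"). Hemoglobin is also measured twice: "to obtain a blood specimen to measure hemoglobin levels prior to beginning therapy", and then "A follow-up blood draw to measure hemoglobin and hematocrit will be completed". The endoscopy score (HES) is likewise rated at both visits. For secondary outcomes, section VIII promises only appropriate analyses.

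**The concern.** With about 12 subjects per arm, the arms will differ somewhat in baseline ESS by chance. A change score removes that difference fully only if follow-up ESS rises one point for each point of baseline ESS. If the slope is smaller, part of the imbalance carries over into the estimated effect as noise. ANCOVA estimates the slope instead of fixing it at one. This matters because the plan reads its CI against clinical meaning, and the minimal important difference is only 0.71 points (section VII, Variables Under Study).

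The conditional mixed model is a secondary matter. Randomization leaves only chance differences between arms, so a trigger that looks for confounders would mostly respond to chance. Without a stated hierarchy, the reported conclusion could depend on which model is shown.

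**Working it through.** **The plan's own figures.** Two-sided Fisher's exact power for 82% against 20% is 77.4% with 11 per arm and 84.5% with 12, so 24 in total reproduces, and 24/0.8 = 30 enrolled. That calculation uses a binary response, so it says nothing about precision on ESS change. The only ESS change SDs are in section V, Recent Study: 1.7 and 0.8 with 10 per arm, approximated data on propranolol gel. Pooled SD = √((1.7² + 0.8²)/2) = 1.329. Then 1.55 ± 2.101 × 1.329 × √(2/10) gives 0.30 to 2.80, and 1.55/1.329 = 1.17, matching the reported CI and effect size of 1.2.

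**Inputs for the comparison**
- From the documents: n = 12 per arm; change SD 1.329; differences of 1.55 (cited trial) and 0.71 (minimal important difference).
- Assumed: ESS SD S = 1.5 to 2. Entry requires ESS of at least 4, which leaves a fraction f of the baseline variance: f = 1 (no narrowing), 0.5 or 0.36. If ESS were normal with mean 4-6 and SD 1.5-2 (also assumed), restriction to 4-10 would leave about 0.35-0.70, so f = 1 is optimistic.

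**t-test.** SE = 1.329 × √(2/12) = 0.542. The 95% CI half-width is 2.074 × 0.542 = 1.125. Noncentral-t power on 22 df is 78.0% at 1.55 and 24.0% at 0.71.

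**ANCOVA.** Let ρ be the slope of follow-up on baseline, which is also the correlation before entry selection.
- Change variance = S²[(1−ρ)²f + 1 − ρ²]. Setting this to 1.329² gives ρ.
- Variance ratio, ANCOVA to change score = (1−ρ²)/[(1−ρ)²f + 1 − ρ²].
- Multiply by 1.05 for expected baseline imbalance (1 + 1/(2n−4), n = 12). Use 21 df, t = 2.080.

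| f | S | ρ | Ratio | Half-width | Power at 1.55 | Power at 0.71 |
|---|---|---|---|---|---|---|
| 1 | 1.5 | 0.608 | 0.804 | 1.036 | 84.3% | 27.5% |
| 1 | 2 | 0.779 | 0.890 | 1.090 | 80.5% | 25.3% |
| 0.5 | 1.5 | 0.559 | 0.876 | 1.082 | 81.1% | 25.6% |
| 0.5 | 2 | 0.766 | 0.938 | 1.119 | 78.4% | 24.2% |
| 0.36 | 1.5 | 0.540 | 0.903 | 1.098 | 79.9% | 25.0% |
| 0.36 | 2 | 0.761 | 0.953 | 1.129 | 77.7% | 23.9% |

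Example (f = 0.5, S = 1.5): SE = 0.542 × √(0.876 × 1.05) = 0.520, and 2.080 × 0.520 = 1.082.

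The ρ values are not the correlations that would be seen in the trial. After selection the correlation is ρ√f/√(ρ²f + 1 − ρ²). At f = 0.5 this is 0.43 to 0.64.

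**Mechanism.** A one-SD chance imbalance in baseline shifts the change-score difference by (1−ρ)·S·√f·√(2/12), which is 0.14-0.19 points at f = 0.5. This is the source of the gain, not an addition to it.

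**Worst case examined.** With ρ = 0.9 and f = 0.36, the ratio is 0.19/(0.0036 + 0.19) = 0.981. Times 1.05 this is 1.030, and power at 1.55 is 76.6%, a loss of 78.0 − 76.6 = 1.4 points. At change SD 1.329 this needs S = 1.329/√0.1936 = 3.02, outside the assumed range.

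**Type I error** (simulation, 200,000 trials per setting, f = 1 and 0.5). With change SDs left at 1.7 and 0.8, rejection under the null is 5.4-5.5% for the t-test and 5.6-5.8% for ANCOVA. With equal SDs, reporting the smaller of the two p-values would give 6.3-7.0%. A fixed rule that adjusts only when baseline ESS has p < 0.10 gives 4.3-4.8%.

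**The case against.** The strongest reply is that nothing here is an error. Randomization makes the t-test valid, it is stated without condition, and the natural reading is t-test first and adjusted model second. All of that stands.

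The size of the gain rests on an ESS SD, and hence a slope, that the documents do not give, and on approximated change SDs for another drug. That also stands. The entry rule makes the most favourable rows doubtful, and the least favourable ones show no gain or a small loss. ANCOVA's type I error under unequal SDs is also slightly higher than that of the t-test.

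Two stronger readings are tempting. A reader might infer that the conditional clause inflates type I error. The documents do not support this: they do not say that the more favourable model will be reported, the factors could be fixed before results are seen, and the fixed rule above does not inflate error. A reader might also infer that ANCOVA reliably lifts power from 78% to about 84%. That figure needs an entry rule that does not narrow the baseline at all.

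The objection does not supply the missing hierarchy. The plan names no covariates, no rule and no primary result for the case where the models differ, and the statistician is not blinded (section VII, Blinding).

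**Conclusion.** The point holds as a cheap improvement with a small, uncertain gain. Against 78.0% for the t-test at 1.55 points, ANCOVA gives 78.4-81.1% with baseline variance halved, 77.7-79.9% with 0.36 left, and 80.5-84.3% with no narrowing. The 95% CI half-width is 1.125 points for the t-test against 1.08-1.12, 1.10-1.13 and 1.04-1.09 in the same order. With either method the interval stays wide beside the 0.71-point minimal important difference.

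These figures assume 12 per arm, change SD 1.33 and ESS SD 1.5-2. Type I error is slightly above 5% for both methods if the change SDs are as unequal as in the cited trial. Naming one primary model in advance is worthwhile whatever the slope turns out to be.

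**What to change.** - Make the single primary analysis an ANCOVA of week-8 ESS (or change in ESS) on arm and baseline ESS. Report the adjusted difference, its 95% CI and the two-sided p-value.
- Remove the conditional confounder clause from the primary analysis.
- Label the t-test and any other adjusted or mixed model as sensitivity analyses that do not replace the primary result.
- Use the same baseline-adjusted form for hemoglobin and HES. No gain has been calculated for these.

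The cost is a few sentences in section VIII and one degree of freedom, with at most 1.4 percentage points of power lost in the worst case examined. No new data, visits or subjects are needed.

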Frequency of Different CYP2D6 Alleles in the Population

The frequency of different CYP2D6 alleles and thus the ability to metabolize timolol was studied in population of 104,509 de-identified patient samples from across the United States between February 2015 and March 2016.(Del Tredici et al. 2018) The frequency distribution of various phenotypes of CYP2D6 alleles was observed to be: ultra-rapid metabolizers (2.2%), normal metabolizers (81%), intermediate metabolizers (11%), and poor metabolizers (6%). Therefore, an estimated total of 17% or 5 subjects otherwise eligible for the study would be expected to be at increased risk of side effects due to timolol compared to the normal metabolizers and therefore will be excluded.

While ophthalmic solution is readily absorbed into the blood stream, CYP2D6 genetic testing is not commonly done for open-angle glaucoma patients prior to initiation of timolol therapy. To prevent cardiovascular side effects, it is recommended that glaucoma patients be screened for coexisting conditions and consideration of genetic phenotypic CYP2D6 status testing if readily available.(Maenpaa and Pelkonen 2016)

In this study, all eligible patients will undergo CYP2D6 testing, ECG, BP, and HR readings at initial visit. Patients with a CYP2D6 allele that is associated with an intermediate or poor metabolizer or an ECG that demonstrates conduction abnormalities, such as second-degree and third-degree AV block and/or clinically significant bradycardia will be excluded from the study. Enrolled patients will be given a blood pressure monitor by the study team and taught how to use it at their baseline visit. They will be instructed to take and report weekly BP and HR to the study team in addition to local or systemic side effects. Patients

will be called at the end of Week 1 and Week 4 of the study to answer any questions or concerns they may have as well as to ask if they have experienced any side effects. During these phone calls, patients will be asked whether they have changed their daily iron supplementation or blood transfusion pattern from baseline. If patients have an increase in nosebleeds for any reason, they will be asked to contact the study team or report to the emergency department, depending on the severity.

Any of the following will be considered an indication to stop the study:

- 1) Asymptomatic systolic BP drop to less than 80 mmHg or a drop of 20% from baseline systolic BP
- 2) Symptomatic blood pressure drop

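### Does the enrolment target of 30 fall short because it makes no allowance for CYP2D6 exclusions?

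*Combined protocol and SAP*

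**What the plan says.** Section VIII (Sample Size) uses Fisher's "exact test in G-Power 3.1.2" with "80% power at the 2-sided alpha level of 0.05". The response rates are 82% and 20%, and both refer to randomized subjects: "We hypothesize a similar response (82%) in our proposed study among subjects randomized to receive timolol gel", with the placebo rate worded the same way. The result is 24 subjects, 12 per arm. The section then states: "Considering a 20% drop out rate, we plan to enroll 30 subjects in the study". The Abstract repeats 24 and 30.

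Section VII (Methods) lists consent, the ECG and the CYP2D6 allele for the initial visit. Randomization comes later: "Upon demonstration that patient does not have the CYP2D6 allele associated with a low or intermediate metabolizer of timolol", and once the questionnaires, examination and laboratory tests are complete.

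Section X (Frequency of Different CYP2D6 Alleles in the Population) cites 11% intermediate and 6% poor metabolizers and concludes that "an estimated total of 17% or 5 subjects otherwise eligible for the study would be expected to be at increased risk of side effects" and will be excluded. It adds that "all eligible patients will undergo CYP2D6 testing, ECG, BP, and HR readings at initial visit", that patients with such an allele or with ECG conduction abnormalities are excluded, and then what enrolled patients will be given.

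No section defines enrolment, gives a number to screen, or says whether pre-randomization exclusions are replaced.

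**The concern.** The step from 24 to 30 is used up entirely by the dropout allowance, yet the protocol expects further losses to genotype testing, and that testing follows consent. The printed figure of 5 is what 17% of 30 gives, so it is natural to think that the authors took the 5 from the 30 and forgot to allow for them.

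If so, about 25 would be randomized and about 20 would be evaluable, fewer than the protocol's own requirement of 24. In a trial this small a few subjects matter: going from 12 to 11 per arm already takes the exact power below 80%. The stated power would then not be delivered even on the protocol's own response rates.

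**Working it through.** **Inputs.** From Section VIII: response rates 0.82 and 0.20, two-sided alpha 0.05, 12 per arm, dropout 20%, target 30. From Section X: excluded phenotypes 11% + 6% = 17%, and the figure of 5. From Section VII: consent and genotype sampling at the same visit, randomization after the result.

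**Reproducing 24.** Unconditional power of the two-sided Fisher exact test, by full enumeration of both binomials at 0.82 and 0.20:

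| Per arm | Power |
|---|---|
| 10 | 67.85% |
| 11 | 77.4% |
| 12 | 84.5% |

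Of these sizes only 12 per arm reaches 80%, so 24 is confirmed.

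**Reproducing 30.** 24 / (1 - 0.20) = 30. This is the correct inflation for dropout and contains no other allowance.

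**Where the 5 comes from.** 0.17 x 30 = 5.1. A base N gives 5 after rounding when 4.5 <= 0.17N < 5.5, that is, for N from 27 to 32. The planned 30 is therefore the likely base.

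**Reading A: 30 is a cap on consents, with no replacement.**
- Randomized: 30 x 0.83 = 24.9
- Evaluable: 24.9 x 0.80 = 19.9, about 20 (10 per arm)
- Power: about 68%

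**Reading B: 30 is the number randomized.**
- Evaluable: 30 x 0.80 = 24 (12 per arm), power 84.5%
- Tested to reach 30: 30 / 0.83 = 36.1, so 36 to 37
- Excluded on genotype: 36.1 - 30 = 6.1, about 6

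**Which reading the text supports.** Four points favour B.

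1. The 5 are described as otherwise eligible, meaning people who fail an eligibility test. Known intermediate or poor metabolizer status is itself exclusion criterion 4 in Section VII.
2. Section X runs in the order testing, exclusion, then enrolled patients.
3. Section VII places randomization after the genotype result, so an excluded person never joins an arm.
4. Section VIII starts from 12 per arm, with response rates among randomized subjects, and inflates for dropout. Someone never assigned to an arm is not naturally a dropout from it.

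The match between 5 and 17% of 30 fits a rough statement of how many carriers to expect when recruiting for a 30-subject trial. It does not show that those people occupy places among the 30, or that recruitment stops at 30 consents.

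**The case for a change.** The best case for a change is that the wording does not settle the matter. Enrolment is never defined, and its use is not decisive: Section VII collects demographics from each enrolled patient, and Section X gives enrolled patients their monitors at the baseline visit, which could be the consent visit. On Reading B the printed 5 is also slightly low, since about 6 exclusions would be expected. If 30 were a consent cap, the chance of reaching 24 evaluable would be about 8% (binomial, n = 30, success probability 0.83 x 0.80 = 0.664).

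Part of this stands. The term is undefined, no screening number is given, and the Reading A arithmetic is right on its own premise. The rest carries less weight. The 8% must be set against the 61% that applies when 30 are randomized (binomial, n = 30, success probability 0.80), because a dropout allowance only meets its target on average. Exclusion of already known carriers before consent could bring the later loss below 17%. The documents give no figure for this, but if 5% to 10% were lost after consent, Reading A would give 30 x 0.95 x 0.80 = 22.8 down to 30 x 0.90 x 0.80 = 21.6 evaluable. ECG exclusions would push the other way, also without a figure. Printing 6 in place of 5 would alter no result or conclusion.

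**Conclusion.** The concern does not call for a change. Both of the protocol's calculations are correct: 24 / 0.80 = 30 and 0.17 x 30 = 5.1. The fall to about 20 evaluable and about 68% power depends on two premises that the documents do not state: that 30 counts consents, and that people excluded on genotype are not replaced. On the reading that the order of events and the construction of the sample size support, 30 are randomized, 24 are expected to be evaluable and no power is lost. The cost is about 6 additional people tested, before any ECG exclusions.

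This rests on the study team treating genotype and ECG exclusions as screen failures and continuing to recruit until 30 are randomized, which is ordinary practice when exclusion precedes randomization. The missing definition and screening number are operational detail; they affect neither the analysis nor its interpretation.

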- 3) *Epistaxis Severity Score (ESS) ≥ 4 and 2 or more nosebleeds per week with a cumulative nosebleed duration of at least 5 minutes per week*
- 4) Stable nasal hygiene and medical regimen for preceding 1 month
- 5) Stable epistaxis pattern over the preceding 3 months

Exclusion Criteria:

- 1) Contraindications for systemic β adrenergic blocker administration
 - a. Hypersensitivity to β adrenergic blockers
 - b. Asthma or bronchospasm
 - c. Congestive heart failure with LVEF <40%
 - d. Hereditary pulmonary arterial hypertension
 - e. Baseline bradycardia (HR <55 beats per minute)
 - f. Sick Sinus Syndrome
 - g. 2nd or 3rd degree heart block, left or right bundle branch block, or bifascicular block
 - h. Uncontrolled diabetes mellitus (most recent HbA1c >9%) or diabetic ketoacidosis within last 6 months
 - i. Hypotension (systolic blood pressure < 90)
- 2) Known hypersensitivity to timolol
- 3) Severe peripheral circulatory disturbances (Raynaud phenomenon)
- 4) Known intermediate or poor metabolizer variant of the liver enzyme CYP2D6
- 5) Current use of any of the following known strong CYP2D6 inhibitors: fluoxetine (Prozac), paroxetine (Paxil), bupropion (Wellbutrin), quinidine, quinine, ritonavir (Norvir), and terbinafine (Lamisil)
- 6) Current use of the following other drugs known to pharmacodynamically interact with timolol: diltiazem, verapamil, digoxin, digitalis, propafenone, disopyramide, clonidine, flecainide, or lidocaine
- 7) Patients currently treated or who plan to initiate treatment with β -blockers
- 8) Use of any anti-angiogenic medication in the last month prior to recruitment, including bevacizumab, pazopanib, thalidomide, or lenalidomide
- 9) Illicit drug use, except marijuana
- 10) Known pheochromocytoma
- 11) Use of anticoagulants, antiplatelet, or fibrinolytic therapies within the last month prior to recruitment, except for low-dose (81 mg or less) of aspirin
- 12) Pregnancy or planned pregnancy in the next 6 months or currently breastfeeding
- 13) Inability to read or understand English

- 14) Inability to complete 8 weeks of therapy for any reason

Eligibility Determination

To determine potential eligibility for the study, the research team will query the medical record based on the following inclusion/exclusion criteria:

- Age (18 years or older)
- Medication history to assess current use of a β -blocker (exclusion)
- Allergy history to timolol (exclusion)
- Changes in epistaxis care in the last month (exclusion)

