- 3) A drop of HR to less than 50/min
- 4) Any clinical signs of heart block
- 5) Grade >2 local or systemic side effects, such as local irritation or an allergic reaction to the medication
- 6) Patient's request or physician's determination of continuing the study to be no longer safe

In the event of a Serious Adverse Event determined by the PI to necessitate the breaking of the blind, the intervention assignment will be revealed by [name] to the medical staff doctor caring for the patient. In the event [name] is unable to be reached in a time needed, to assure the safety of the subject, the blind can be broken by [name] or [name] and information will be shared with the medical staff assuming care for the research subject.

XI. Data and Safety Monitoring

The specific monitoring plan for this study is based on the potential risk of participation and size and complexity of the planned investigation. Based on these considerations, this study will have a monitoring board comprised of [name], [name], [name], and [name], the study biostatistician. The monitoring board will meet to review data at least every 6 months. All reports of a Serious Adverse Event (SAE) or an Unexpected Adverse Event will be investigated by the monitoring team and reported to Washington University HRPO according to the reporting requirements.

XII. Ethical considerations

While patients will be randomly selected to receive timolol, an FDA-approved drug, the efficacy and safety, including local and/or systemic reactions, are largely unknown when applied in topical gel form. Patients will be informed in the informed consent process that they may or may not personally benefit from the study and that the data obtained from the study will be used to inform the future care of HHT patients with epistaxis. There will be phone assistance available 24/7 during the study period to report any possible adverse reactions. To reduce the risk of breach of confidentiality, all data forms with identifying information will be kept in locked cabinets and only members of the study team will have access to secured files. There are no financial conflicts of interest.

XIII. REFERENCES

- Albinana, V., L. Recio-Poveda, R. Zarrabeitia, C. Bernabeu, and L.M. Botella. 2012. Propranolol as antiangiogenic candidate for the therapy of hereditary haemorrhagic telangiectasia. *Thromb Haemost* 108: 41-53.

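### Subjects who meet a stop criterion have no assured week-8 ESS, so the primary comparison defaults to completers, with bias of unknown direction

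*Combined protocol and SAP*

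**What the plan says.** Section X (Assessment of Treatment Safety) gives six criteria under the line "Any of the following will be considered an indication to stop the study". They are an asymptomatic fall in systolic pressure (absolute or relative to baseline), a symptomatic fall, "A drop of HR to less than 50/min", signs of heart block, side effects above Grade 2, and the subject's request or the physician's judgement. The last one shows that the list applies to one subject at a time, not to the trial. Nothing says whether the subject gives up only the gel or also the remaining assessments.

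Section VII (Methods) places the follow-up ESS, HES, CGI and hemoglobin at one visit: "After 8 weeks of intervention, subjects will be asked to return to clinic". The contacts at Weeks 1 and 4 are telephone calls. The daily log records nosebleeds, but it is not an ESS and the primary analysis does not use it. No early-termination visit or off-gel week-8 visit is described.

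Section VIII compares the change in ESS by an independent-sample t-test, with a mixed model only if confounders are found. It names no analysis population, missing-data method or sensitivity analysis. Loss is dealt with by numbers alone: "Considering a 20% drop out rate, we plan to enroll 30 subjects in the study".

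**The concern.** A t-test on change needs a baseline and a week-8 value. If meeting a stop criterion ends participation before the week-8 visit, that subject has no change score and drops out of the primary comparison by default.

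This differs from ordinary dropout because the first four criteria (two on blood pressure, one on heart rate, one on heart block) are effects that the protocol itself attributes to timolol, in Section V, Section X and Appendix 6. Loss could therefore be more frequent on timolol than on placebo. Randomisation protects the comparison of everyone randomised; it does not protect a comparison of those who remain when remaining depends on treatment. Enrolling 30 to keep 24 restores the number of subjects, not the balance between the arms. An outcome that was never collected also cannot be recovered at the analysis stage.

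**Working it through.** **1. The plan's own figure.** Section VIII uses Fisher's "exact test in G-Power 3.1.2" "with 80% power at the 2-sided alpha level of 0.05", with 82% against 20% responding. Exact enumeration gives power of 84.5% at 12 per arm and 77.4% at 11, so 12 per arm (24 in total) reproduces. Then 24 / (1 − 0.20) = 30. The plan thus allows for 6 of 30 subjects without an outcome.

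**2. Size of the bias.** The documents give no stop rate for this gel and no timolol ESS change, so what follows is illustration under assumptions.

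- Proxy means and SDs come from the randomised propranolol trial in Section V: 2.03 (SD 1.7) and 0.48 (SD 0.8), 10 per arm. Check: SE = √(1.7²/10 + 0.8²/10) = 0.594, and 1.55 ± 2.10 × 0.594 gives 0.30 to 2.80, as stated there.
- Assume 15 randomised per arm, *k* stops on timolol and none on placebo, and take 2.03 and 0.48 as the means in those observed. The completer difference is 2.03 − 0.48 = 1.55.
- Let *S* be the week-8 change that the stoppers would show if measured. Completer difference minus all-randomised difference = (*k*/15) × (2.03 − *S*).

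| Assumed *S* | *k* = 1 | *k* = 3 | *k* = 6 |
|---|---|---|---|
| 0.48 (like placebo) | +0.10 | +0.31 | +0.62 |
| 0 (no change) | +0.14 | +0.41 | +0.81 |
| 2.03 (like completers) | 0 | 0 | 0 |
| 3.73 (1 SD better: 2.03 + 1.7) | −0.11 | −0.34 | −0.68 |

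Plus means that completers overstate the difference. The minimal important difference in Section VII is 0.71. To be biased by that much, 0.71/2.03 = 35% (no change) to 0.71/1.55 = 46% (like placebo) of the timolol arm would have to stop.

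**3. Effect on the test when there is no true difference.** Simulation with 15 per arm, SD √((1.7² + 0.8²)/2) = 1.33 and 100,000 runs. Stopping is in the timolol arm only, except in the last row.

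| Stopping | Mean bias | Two-sided error |
|---|---|---|
| 20%, poor responders tend to stop (correlation 0.5) | +0.23 | 7.1% |
| 20%, unrelated to outcome | 0 | 4.9% |
| 20%, good responders tend to stop | −0.23 | 7.1% |
| 40%, either direction | ±0.43 | 11.1% |
| 20% in both arms, same relation to outcome | 0 | 4.9% |

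In the first row, 6.3% of runs are significant in favour of timolol, against a nominal 2.5%.

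**4. A possible example in the protocol.** The earlier timolol-drop study (Section V) treated 12 patients, one of whom was removed after hypotension, bradycardia and heart failure. Section VIII then reports that "9 of the 11 subjects (82%) experienced a reduction in the severity of bleeds". If the removed patient is the missing twelfth, which is an inference, and counts as a failure, 9/11 = 82% becomes 9/12 = 75%. Power at 12 per arm then falls from 84.5% to 71.6%.

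**The case against.** The wording may mean only that the gel is stopped and the week-8 visit is kept; the design figure, which might show this, is not in the copy reviewed. That reading is open, and it is why the point concerns an unresolved wording and not a stated rule of withdrawal.

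Stops may also be few. Section VII excludes conduction block, low blood pressure, a heart rate under 55 and known reduced CYP2D6 metabolism, and Section X tests for the last. Section X reports heart-rate change as less likely with 0.1% hydrogel than with 0.5% aqueous drops, and the propranolol trial saw no cardiovascular effects. These points limit the likely size. They do not remove the issue: a subject entering at 55 beats/min meets the heart-rate criterion after a fall of 6 (55 − 6 = 49). Not every criterion is specific to the drug either; local irritation, the subject's request or a chance low home reading can occur on placebo.

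The exclusion "Inability to complete 8 weeks of therapy for any reason" might be read as evidence of a completer design. It is an entry criterion and says nothing about later loss.

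Two stronger readings are tempting. The first is that the result would favour timolol. The cardiac events in Section V began on day 2 and within 3 weeks, and the ESS here refers to the past month, so an early stopper's week-8 score would describe time off drug. That makes a placebo-like score plausible. But subjects who absorb more could have both more beta-blockade and more benefit, and the documents give no direction. The second is a 36% overstatement: 0.8 × 2.03 − 0.48 = 1.14, and 1.55/1.14 = 1.36. This puts a 20% loss in the timolol arm alone, 3 of 30 or 10% overall, whereas the protocol's 20% is 6 of 30 across both arms. It also treats all dropout as drug-related and uses means from another drug, which the protocol does not describe as completer means. Equal 20% loss with no gain in those lost gives 0.8 × 1.55 = 1.24, but that gap comes wholly from the zero-gain assumption, not from unequal loss.

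**Conclusion.** The concern holds as a gap in follow-up and analysis. Followed as written, the plan can lose the week-8 ESS of anyone who meets a stop criterion, and its default is then a completer analysis with possibly unequal loss and bias of unknown sign.

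On the proxy means, and with stops on timolol only, the overstatement is about 0.10 to 0.14 ESS points for one stop and 0.31 to 0.41 for three, if stoppers score like placebo or do not change. It is zero if stopping is unrelated to ESS change, and it turns against timolol if better responders stop. One stop matters little against a minimal important difference of 0.71; several would matter. This is a cheap improvement, worth making before enrolment because the missing values cannot be collected afterwards. It implies no view on the clinical thresholds.

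**What to change.** Leave the clinical stop criteria untouched. Reconcile Sections VII and X so that meeting a criterion does not by itself end outcome collection. Seek the week-8 ESS, hemoglobin, HES and CGI from every randomised subject who still consents, whether or not still on gel, and record the date and reason for stopping.

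In Section VIII, state that the primary comparison includes all randomised subjects in their assigned arm. Use multiple imputation where the ESS is truly missing. Add a tipping-point analysis that shifts the imputed values in both directions, so that bias for or against timolol would show.

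The cost is wording, up to about six off-gel week-8 visits (20% of 30), and possibly a smaller effect estimate, because it would include subjects no longer treated.
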